7.3.3 Efficacy Endpoints Based on Investigator Assessment

The Investigator will assess efficacy at specific study visits according to the response criteria for MM as defined in section 18.3 of the study protocol version valid at the time of the assessment. All of the criteria are based on the International Myeloma Working Group (IMWG) Uniform Response Criteria [6], except for MR, which is based on the (adopted) European Group for Blood and Marrow Transplantation (EBMT) criteria [7].

The response evaluation of the Investigator is based on the serum and urine M-protein levels, and, where applicable, the serum FLC level, and FLC ratio.

The categories of overall tumor response assessment of the Investigator will be as follows:

- sCR – Stringent Complete Response
- CR - Complete Response
- VGPR - Very Good Partial Response
- PR - Partial Response
- MR - Minimal Response
- SD - Stable Disease
- PD - Progressive disease
- Missing (if response assessment is not done)

In case of progressive disease, the date of progression will be given by the Investigator.

All responses need 2 consecutive assessments, ideally being confirmed at Day 1 of the next cycle. Thus all endpoints defined to evaluate responses per-subject across time points (see section 7.3.3.2 and 7.3.3.3) will include confirmed responses only.

For all endpoints where dates are used in the derivations (e.g. date of first response, date of first

progression), the following dates will be taken into consideration to determine the time point each response assessment refers to:

- Date of assessment or date of visit, whichever is earlier if the assessment is non-PD (this approach is chosen as the assessment is sometimes done retrospectively and not at the date of the visit)
- date of progression given by the Investigator in the field “Date of Progression” in the response assessment form if the assessment is PD

In case any non-study anti-MM treatments are given before end of study (see also section 8.3, it is regarded as protocol non-compliance. Tumor assessments after start of non-study anti-MM treatment will not be taken into account for any of the derived efficacy variables described below. In case the start date of non-study anti-MM treatment is incomplete, an imputed start date will be used in all derivations. The imputed start date will always be the first possible start date, but after the end-of-study (EOS) visit. For example, in case day is missing, but month and year are complete, the first day of the month will be taken if after EOS, otherwise date of EOS + 1.

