7.3.3.1 Responses by subject and visit

The following variables will be derived by visit based on the overall tumor assessment of the Investigator:

Any response (PR or better) (yes/no) by visit:

- yes, if tumor response assessment is sCR, CR, VGPR, or PR
- no, if tumor response assessment is MR, SD, PD or Missing

Any clinical benefit (MR or better) (yes/no) by visit:

- yes, if tumor response assessment is sCR, CR, VGPR, PR or MR
- no, if tumor response assessment is SD, PD or Missing

Any disease control (SD or better) (yes/no) by visit:

- yes, if tumor response assessment is sCR, CR, VGPR, PR, MR or SD
- no, if tumor response assessment is PD or Missing

7.3.3.2 Responses derived per-subject across time points:

The subsequent variables will be derived per-subject across time points, based on the overall tumor assessment of the Investigator.

Best Overall Response (BOR): The best overall response will be defined as the best response across all time points. The best possible overall response is sCR, followed by CR, VGPR, PR, MR, SD, and PD.

To be assigned a status of sCR, CR, VGPR, PR, MR, SD, the first assessment must be confirmed by the next consecutive non-missing assessment (missing values will not be taken into account). Both assessments must show a status of sCR, CR, VGPR, PR, MR or SD, and the assigned confirmed status will be the weaker status of both assessments.

A single progression of disease (PD) assessment which did not cause a discontinuation of

treatment and which has been disproven by the next consecutive non-missing tumor assessment will not be considered in the evaluation of best overall response. If no post-baseline confirmed response assessment or PD is available, then the best overall response will be “Not Evaluable” (NE).

Secondary efficacy endpoint variables:

Any response (yes/no) in study:

- yes, if best overall response is sCR, CR, VGPR or PR
- no, if best overall response is MR, SD, PD or NE

The **Overall response rate (ORR)**, defined as the proportion of subjects who meet the criteria of confirmed sCR, CR, PR or VGPR at any time during study, will be calculated from this variable.

Additional efficacy variables:

Any clinical benefit (yes/no) in study:

- yes, if best overall response is sCR, CR, VGPR, PR or MR
- no, if best overall response is SD, PD or NE

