7.3.3.3 Time-related efficacy endpoints

With respect to the time-related efficacy endpoints defined subsequently, a single PD assessment which did not cause a discontinuation of treatment and which has been disproven by the next consecutive non-missing tumor assessment will not be considered when determining the date of first progression and the censoring variables.

Thus, the date of progression used for the derivations will be the date of progression related to the first PD assessment that fulfills at least 1 of the following criteria:

- the next consecutive non-missing tumor assessment is also PD
- the PD assessment is the last tumor assessment in the study

The start date for sCR, CR, VGPR, PR, MR and SD is defined as the date of the first time point at which the response was noted, provided that the response was confirmed at a later time point (as described in section 7.3.3.2). However, a response followed by ≥ 2 non-confirming consecutive non-missing planned response assessments will not be considered for the determination of the first date at which the response was noted.

The date of death due to progression is the stop date of AEs with a fatal outcome and a preferred AE term “Disease progression” or “Multiple myeloma”.

All time-related efficacy endpoints defined below will be reported in months.

Secondary efficacy endpoint variables:

Duration of response (DoR): The duration of response will be calculated in the subgroup of subjects showing confirmed sCR, CR, VGPR or PR. Duration of response will be defined as the time from date of first response (sCR, CR, VGPR or PR) until date of progression or death due to progression (as defined above) whichever is documented first. For censoring rules see Table 2.

Time to progression (TTP): Time to progression will be defined as the time from Cycle 1, Day 1 until date of progression or death due to progression (as defined above) whichever is documented first. For censoring rules see Table 2.

Table 2: Censoring Rules for DoCB, DoR and TTP

Situation	Date of Progression or Censoring	Outcome
Disease Progression	Date of progression	Progressed
No baseline tumor assessment	Date of first treatment	Censored
No disease progression	Date of last tumor assessment	Censored
Subject received non-study MM treatment before disease progression	Date of last tumor assessment prior to non-study treatment	Censored

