In case any new anti-MM treatments are given before end of study (see also section 8.3), this will be regarded as protocol non-compliance. M-protein values measured after start of new anti-MM treatment will be flagged in listings. Moreover, these will be excluded from tables and will not be taken into account when deriving relative changes from baseline to post-baseline nadir.

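### Incomplete start dates of non-study anti-myeloma therapy are always imputed to after EOS, which disables the SAP's own exclusion and censoring rules when that therapy began before EOS

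*SAP*

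**What the plan says.** The paragraph in SAP 7.3.3 opens with this case: "In case any non-study anti-MM treatments are given before end of study". It calls such treatment protocol non-compliance and sets the consequence: "Tumor assessments after start of non-study anti-MM treatment will not be taken into account for any of the derived efficacy variables described below".

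Partial dates follow: "In case the start date of non-study anti-MM treatment is incomplete, an imputed start date will be used in all derivations". The rule is: "The imputed start date will always be the first possible start date, but after the end-of-study (EOS) visit". For a known month with a missing day, the SAP spells it out: "the first day of the month will be taken if after EOS, otherwise date of EOS + 1". There is no exception for therapy known to have started before EOS.

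Other rules need the same start date:

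- Tables 2 and 3 (section 7.3.3.3) censor DoR, TTP, DoCB and PFS, when non-study treatment precedes progression, at the "Date of last tumor assessment prior to non-study treatment".
- Section 7.3.4 says of M-protein values measured after new therapy starts that "these will be excluded from tables and will not be taken into account when deriving relative changes from baseline to post-baseline nadir".
- Section 9.2 sets by-visit responses to missing by reference to the start of new anti-myeloma therapy.

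**The concern.** The first half of the paragraph needs a start date that can fall before EOS. The second half makes that impossible whenever the date is incomplete. A month that ended before EOS is overwritten with a date that the record itself rules out.

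Since "The best overall response will be defined as the best response across all time points" (section 7.3.3.2), assessments made under another myeloma drug then feed best overall response and ORR. They can also set the M-protein nadir and move the PFS, TTP or DoR date. Effects of another drug would be reported as effects of the study regimen.

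**Working it through.** The documents attach no figure to this rule, so there is none to reproduce. The check is logical, followed by an illustration on assumed dates.

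**Logic.** Imputed start = first day of the recorded month if later than EOS, otherwise EOS + 1. The imputed start is therefore never earlier than EOS + 1. Protocol 10.1.14 makes EOS the last visit, with a response assessment, so every on-study assessment falls on or before EOS. The number of assessments after the imputed start is zero for every incomplete date.

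**Illustration.** Assumed: Cycle 1 Day 1 on 4 Jan 2016; assessments every 28 days (protocol Table 2: Day 1 of each cycle) on 1 Feb, 29 Feb, 28 Mar, 25 Apr, 23 May and 20 Jun; EOS on 20 Jun; no progression; day of start missing. PFS time = (censoring date − Cycle 1 Day 1 + 1)/30.4375. The divisor is my assumption because the SAP's is masked.

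| Recorded start | SAP date | Excluded; PFS censored | Earliest compatible date | Excluded; PFS censored | Difference (months) |
|---|---|---|---|---|---|
| Mar 2016 | 21 Jun | 0; 20 Jun, 169/30.4375 = 5.55 | 1 Mar | 4; 29 Feb, 57/30.4375 = 1.87 | 3.68 |
| Apr 2016 | 21 Jun | 0; 5.55 | 1 Apr | 3; 28 Mar, 85/30.4375 = 2.79 | 2.76 |
| May 2016 | 21 Jun | 0; 5.55 | 1 May | 2; 25 Apr, 113/30.4375 = 3.71 | 1.84 |
| Jun 2016, recorded as on-study | 21 Jun | 0; 5.55 | 1 Jun | 1; 23 May, 141/30.4375 = 4.63 | 0.92 |
| Jul 2016 | 1 Jul | 0; 5.55 | 1 Jul | 0; 5.55 | 0 |

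**Response.** Take the March row and assume PR on 25 Apr and 23 May only. As written, this is a confirmed responder. With 1 Mar as the start, the last usable assessment is 29 Feb and the subject is not a responder. Section 7.3.3.2 requires confirmation by the next non-missing assessment, so one assessment under the other drug cannot create a response alone, but it can confirm an earlier one. Added later assessments cannot undo a pair already confirmed, so retention cannot lower a confirmed best response of PR or better. SAP section 5 sets a minimum of 9 subjects per recommended-dose group: 1/9 = 11.1 percentage points of ORR.

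**PFS and TTP.** Change one assumption: 20 Jun is progression. As written, the subject has an event at 5.55 months. With 1 Mar, the subject is censored at 1.87 months. Here the SAP rule adds an event. In the table, it only delays a censoring time.

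**Other partial-date rules in the SAP.** For concomitant medication (8.3) and adverse events (10.2), recorded months and years are respected and only the unknown part is resolved by convention. The rule in 7.3.3 alone overrides a recorded month.

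**The case against.** The strongest defence is that the rule was evidently written for therapy that follows EOS. SAP 8.3 captures the first subsequent treatment and its start date, and protocol 10.1.14 asks that EOS precede any new therapy. For a recorded month equal to or later than the EOS month, the floor is then sensible. Harm needs several failures together: prohibited therapy on study, a subject not withdrawn (protocol 8.7.1, SAP 8.3), further assessments although follow-up should stop at new therapy (protocol 10.1.12), and an incomplete date. Protocol 9.4 also asks that the medical monitor be contacted before any myeloma-related therapy starts.

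This stands as an argument about frequency. It does not rescue the rule. The paragraph, the rows in Tables 2 and 3 and the exclusion in 7.3.4 exist for this non-compliance, so they cannot presuppose compliance. Overlap is plausible: subjects off treatment without progression are assessed every 4 weeks, and EOS falls at least 28 days after the last dose.

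A reader might infer that the error flatters every efficacy endpoint. The documents do not support that. It holds for ORR, but under Tables 2 and 3 a retained progression is an event where the subject would otherwise have been censored. Nor do the month differences in the table estimate a change in median PFS; each is a shift in one subject's censoring time.

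**Conclusion.** The rule is wrong as written for one group: subjects whose non-study therapy began before EOS and whose start date is incomplete. For them the exclusion of later tumor assessments and the Table 2–3 censoring cannot act. The same holds for the M-protein exclusion in 7.3.4, reading the instruction to use the imputed date in all derivations as reaching that section, which gives no date rule of its own.

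ORR can only be inflated, by 11.1 points per false responder in a group of 9. PFS and TTP can be affected in either direction. In the illustration, 1 to 4 assessments are wrongly kept and censoring moves 0.9 to 3.7 months later; these sizes rest on assumed dates.

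Complete dates are handled correctly, as is therapy that truly follows EOS. The documents do not say how many subjects are affected; the number is probably small. A reader might also infer a threat to the dose recommendation, but the primary endpoints (MTD or recommended dose and regimen, adverse events, immunogenicity) do not use this date. The endpoints affected are secondary or additional and descriptive. The SAP should be corrected because the error is definite and cheap to repair.

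**What to change.** In SAP 7.3.3:

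1. Apply the EOS + 1 floor only to Subsequent anti-MM Treatment entries whose recorded parts allow a date after EOS.
2. For therapy recorded as given during the study, or whose recorded parts place it before EOS, impute the earliest date compatible with those parts, not before Cycle 1 Day 1.
3. Use that date for the tumor-assessment exclusion, the Table 2–3 censoring and the M-protein exclusion in 7.3.4.
4. Add a sensitivity analysis using the latest compatible date.

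The cost is a sentence or two of SAP text, a few lines of code and one repeated analysis. Affected subjects are censored earlier. With a known month the two analyses should be close: in the March example, the latest date, 31 Mar, excludes 3 assessments instead of 4 and censors at 2.79 instead of 1.87 months. With only the year the earliest-date rule is harsh. If on-study therapy is recorded as 2016 only, the start becomes 4 Jan 2016, all six assessments drop and best overall response becomes not evaluable, even if a genuine response came first. The sensitivity analysis will show how far results depend on such cases.

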7.3.3.1 Responses by subject and visit

The following variables will be derived by visit based on the overall tumor assessment of the Investigator:

Any response (PR or better) (yes/no) by visit:

- yes, if tumor response assessment is sCR, CR, VGPR, or PR
- no, if tumor response assessment is MR, SD, PD or Missing

Any clinical benefit (MR or better) (yes/no) by visit:

- yes, if tumor response assessment is sCR, CR, VGPR, PR or MR
- no, if tumor response assessment is SD, PD or Missing

Any disease control (SD or better) (yes/no) by visit:

- yes, if tumor response assessment is sCR, CR, VGPR, PR, MR or SD
- no, if tumor response assessment is PD or Missing

7.3.3.2 Responses derived per-subject across time points:

The subsequent variables will be derived per-subject across time points, based on the overall tumor assessment of the Investigator.

Best Overall Response (BOR): The best overall response will be defined as the best response across all time points. The best possible overall response is sCR, followed by CR, VGPR, PR, MR, SD, and PD.

To be assigned a status of sCR, CR, VGPR, PR, MR, SD, the first assessment must be confirmed by the next consecutive non-missing assessment (missing values will not be taken into account). Both assessments must show a status of sCR, CR, VGPR, PR, MR or SD, and the assigned confirmed status will be the weaker status of both assessments.

A single progression of disease (PD) assessment which did not cause a discontinuation of

treatment and which has been disproven by the next consecutive non-missing tumor assessment will not be considered in the evaluation of best overall response. If no post-baseline confirmed response assessment or PD is available, then the best overall response will be “Not Evaluable” (NE).

Secondary efficacy endpoint variables:

Any response (yes/no) in study:

- yes, if best overall response is sCR, CR, VGPR or PR
- no, if best overall response is MR, SD, PD or NE

The **Overall response rate (ORR)**, defined as the proportion of subjects who meet the criteria of confirmed sCR, CR, PR or VGPR at any time during study, will be calculated from this variable.

Additional efficacy variables:

Any clinical benefit (yes/no) in study:

- yes, if best overall response is sCR, CR, VGPR, PR or MR
- no, if best overall response is SD, PD or NE

The **Clinical benefit rate (CBR)**, defined as the proportion of subjects who meet the criteria of confirmed CR, PR, VGPR or MR at any time during study, will be calculated from this variable.

Any disease control (yes/no) in study:

- yes, if best overall response is sCR, CR, VGPR, PR, MR or SD
- no, if best overall response is PD or NE

The **Disease control rate (DCR)** defined as the proportion of subjects who meet the criteria of confirmed sCR, CR, VGPR, PR, MR or SD at any time during study, will be calculated from this variable.

7.3.3.3 Time-related efficacy endpoints

With respect to the time-related efficacy endpoints defined subsequently, a single PD assessment which did not cause a discontinuation of treatment and which has been disproven by the next consecutive non-missing tumor assessment will not be considered when determining the date of first progression and the censoring variables.

Thus, the date of progression used for the derivations will be the date of progression related to the first PD assessment that fulfills at least 1 of the following criteria:

- the next consecutive non-missing tumor assessment is also PD
- the PD assessment is the last tumor assessment in the study

The start date for sCR, CR, VGPR, PR, MR and SD is defined as the date of the first time point at which the response was noted, provided that the response was confirmed at a later time point (as described in section 7.3.3.2). However, a response followed by ≥ 2 non-confirming consecutive non-missing planned response assessments will not be considered for the determination of the first date at which the response was noted.

The date of death due to progression is the stop date of AEs with a fatal outcome and a preferred AE term “Disease progression” or “Multiple myeloma”.

All time-related efficacy endpoints defined below will be reported in months.

Secondary efficacy endpoint variables:

Duration of response (DoR): The duration of response will be calculated in the subgroup of subjects showing confirmed sCR, CR, VGPR or PR. Duration of response will be defined as the time from date of first response (sCR, CR, VGPR or PR) until date of progression or death due to progression (as defined above) whichever is documented first. For censoring rules see Table 2.

Time to progression (TTP): Time to progression will be defined as the time from Cycle 1, Day 1 until date of progression or death due to progression (as defined above) whichever is documented first. For censoring rules see Table 2.

Table 2: Censoring Rules for DoCB, DoR and TTP

Situation	Date of Progression or Censoring	Outcome
Disease Progression	Date of progression	Progressed
No baseline tumor assessment	Date of first treatment	Censored
No disease progression	Date of last tumor assessment	Censored
Subject received non-study MM treatment before disease progression	Date of last tumor assessment prior to non-study treatment	Censored
Death from other causes than disease progression, without documented disease progression before	Date of last tumor assessment	Censored
Death caused by disease progression between adequate assessments	Date of death	Progressed
Death caused by disease progression or progression after > 65 days (2x 29-day cycle +7 days) after last tumor response assessment (representing the time interval of 2 or more consecutive missed tumor response assessments)	Date of last tumor assessment	Censored

Progression-free survival (PFS): Progression-free survival will be defined as the time from

Cycle 1, Day 1 until date of progression (as defined above) or date of death, whatever occurs earlier, or date of censoring (as defined below). For censoring rules see Table 3.

Table 3: Censoring Rules for PFS

Situation	Date of Progression or Censoring	Outcome
Disease progression	Date of progression	Progressed
No post-baseline tumor assessment	Date of first treatment	Censored
No disease progression	Date of last tumor assessment	Censored
Subject received non-study MM treatment before disease progression	Date of last tumor assessment prior to non-study treatment	Censored
Death before any date of PD assessment	Date of death	Progressed
Death between adequate assessments	Date of death	Progressed
Death or progression after > 65 days (2x 29-day cycle +7 days) after last tumor response assessment (representing the time interval of 2 or more consecutive missed tumor assessments)	Date of last tumor assessment	Censored

Additional time to event variables:

Duration of clinical benefit (DoCB): The duration of clinical benefit will be calculated in the subgroup of subjects showing confirmed sCR, CR, VGPR, PR or MR. Duration of clinical benefit will be defined as the time from date of first clinical benefit (sCR, CR, VGPR, PR or MR) until date of progression or death due to progression (as defined above), whichever is documented first. For censoring rules see Table 2.

Additionally, the DoR of sCR/CR and sCR/CR/VGPR according to the above defined rules will be reported separately.

Time to next treatment (TTNT): TTNT will be defined as the time from Cycle 1, Day 1 until start date of new anti-MM treatment as documented at the end of trial visit under “Subsequent anti-MM Treatment” or date of death. Subjects with no documented start date for a subsequent anti-MM treatment and no documented date of death will be considered censored using the date of the last visit.

Event-free survival (EFS): EFS will be defined as the time from Cycle 1, Day 1 until date of progression, date of death, or date of discontinuation of treatment for any reason (e.g. toxicity, subject preference, or initiation of a new treatment without documented progression), whichever occurs earlier. Subjects still on treatment, without disease progression, will be censored at the date of the last available tumor assessment.

Additional time to event variables for the subgroup of responders:

Time to first response: Time to first response will be defined as the time from Cycle 1, Day 1 until start date of first response (sCR, CR, VGPR or PR).

Time to best response: Time to best response will be defined as the time from Cycle 1, Day 1 until best response (sCR, CR, VGPR or PR).

Time to first clinical benefit: Time to first clinical benefit will be defined as the time from Cycle 1, Day 1 until first clinical benefit (sCR, CR, VGPR, PR or MR).

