- Severe: Incapacitating (causes inability to perform usual activity or work)

The toxicity grade of AEs will be graded according to the NCI CTCAE (version 4.0 of May 28, 2009) using the following definitions:

- Grade 1: Mild; asymptomatic or mild symptoms; clinical or diagnostic observations only; intervention not indicated.
- Grade 2: Moderate; minimal, local or non-invasive intervention indicated; limiting age-appropriate instrumental activities of daily living (refers to

preparing meals, shopping for groceries or clothes, using the telephone, managing money, etc.).

- Grade 3: Severe or medically significant but not immediately life-threatening; hospitalization or prolongation of hospitalization indicated; disabling; limiting self-care activities of daily living.
- Grade 4: Life-threatening consequences; urgent intervention indicated.
- Grade 5: Death related to AE.

The causal relationship of all AEs to IMP intake will be judged as either suspected or not suspected. If no relationship has been provided by the investigator, the event will be considered as related to study drug and notified to authorities according to regulatory reporting requirements.

In addition to the investigator's own description of the AEs, each AE will be encoded by the sponsor (or its delegate) according to the current version of the Medical Dictionary for Regulatory Activities (MedDRA).

All non-serious AEs must be followed up for a final outcome until resolution or until the EOS visit. An outcome of "unknown" is not considered to be an acceptable final outcome. An outcome of "not yet resolved" is an acceptable final outcome for non-serious AEs at the end of a subject's participation in a study. SAEs must be followed up for a final outcome until resolution or, if resolution becomes unlikely, until stabilization or death. This includes obtaining information on recovery and any sequelae and, in case of a fatal outcome, the cause of death. For SAEs which are due to progression of MM, follow-up only until the end of subject's participation in the study is acceptable.

will report all reportable events to all competent authorities (including the European Medicines Agency [EMA]), IECs or Institutional/Independent Review Boards (IRBs), and investigators as required by local regulations and Premier Research standard operating procedures (SOPs).

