10.2 Adverse Events

All TEAEs and SAEs will be coded using MedDRA (MedDRA Version 20.1, and updated to the newest version 23.0 for the follow-up analyses).

The body systems 'Blood and lymphatic system disorders' and 'Investigations' will be combined for the purpose of analysis. Moreover, all preferred terms from those two body systems that are subsequently listed in the same row will be combined:

- Red blood cell count decreased / Haemoglobin decreased / Haematocrit decreased / Mean cell volume decreased / Anaemia
- Fibrin D dimer increased / International normalised ratio increased / Prothrombin time shortened / Coagulopathy
- Eosinophil count increased / Eosinophilia
- Blood fibrinogen increased / Hyperfibrinogenaemia
- White blood cell count increased / Leukocytosis
- White blood cell count decreased / Leukopenia
- Lymphocyte count decreased / Natural killer cell count decreased / CD4 lymphocytes decreased / B-lymphocyte count decreased / Lymphopenia
- Monocyte count decreased / Monocytopenia
- Neutrophil count decreased / Neutropenia
- Neutrophil count increased / Neutrophilia
- Plasma cells increased / Plasmacytosis
- Platelet count decreased / Thrombocytopenia

TEAEs are defined as AEs occurring or worsening after the start (date and time) of the first study treatment (any IMP) and up to 28 days after the last study treatment including all treatment cycles (treatment emergent period). However, AEs occurring or worsening later than 28 days after the last treatment with study drug are defined as treatment emergent if these are considered to be related to the study drug.

If the start date and time of an AE are partially or completely missing, the AE will be assumed to be treatment-emergent if it cannot be definitely shown that the AE did not occur or worsen during the treatment-emergent period (worst case approach). Missing dates and times will not be replaced.

Thus, the following approach will be taken:

- If the start time of an AE is missing but the start date is complete, an AE will only be excluded from TEAEs if the start day is before the day of first treatment or the start day is after the end day of the treatment-emergent period.
- If the start time and day are missing but the start month is complete, an AE will only be excluded from TEAEs if the start month is before the month of first treatment or the start

month is after the end month of the treatment-emergent period or if stop date/time is before start of first treatment.

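### In TTP, DoR and DoCB, a death counts as due to progression only if the fatal AE carries one of two preferred terms, so a myeloma death coded to a complication is censored

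*SAP*

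**What the plan says.** SAP 7.3.3.3 gives one operational definition: "The date of death due to progression is the stop date of AEs with a fatal outcome and a preferred AE term" of "Disease progression” or “Multiple myeloma". TTP and DoR run "until date of progression or death due to progression (as defined above) whichever is documented first", and DoCB uses the same definition. In SAP Table 2, the situation "Death from other causes than disease progression, without documented disease progression before" is censored at the date of the last tumour assessment. Death caused by progression between adequate assessments is an event on the date of death. Progression, or death from it, more than 65 days after the last assessment is censored at that assessment.

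Protocol 12.1 sets the follow-up required for SAEs: "This includes obtaining information on recovery and any sequelae and, in case of a fatal outcome, the cause of death". The SAP does not use that information for these endpoints.

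**The concern.** The rule lets the coded name of the fatal event stand in for the reason the subject died. The two can differ. Protocol 12.1 asks sites to record events as diagnoses where possible, so a fatal complication of progressing myeloma, such as renal failure, may be reported and coded as that complication. The death then fails the match although the disease caused it.

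The subject is censored shortly before an event that belongs to the endpoint. Kaplan-Meier methods assume that censored subjects have the same future risk as those who remain, and here that assumption fails in a known direction: TTP, DoR and DoCB look longer than they are. Groups are small (SAP 5 gives a minimum of 9 subjects at a recommended dose), so one such death can move an estimate visibly.

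**Working it through.** The plan states no figure for this point. The check is a trace through the rules, followed by two illustrations on assumed inputs.

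**1. Does such a death fail the match?** Suppose a subject without recorded PD dies of hypercalcaemia caused by the myeloma. Protocol Table 14 accepts hypercalcaemia attributable solely to the plasma cell disorder as a PD criterion. If the fatal AE is coded to hypercalcaemia and no PD assessment is entered, neither term matches. The death falls into the other-causes row of Table 2 and is censored.

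**2. Is there another route?** None is given. Table 2 speaks of death caused by progression, but its only working definition is the term match. The merging of preferred terms in SAP 10.2 covers blood and investigation terms only. No step classifies deaths, although SAP 10.1 lets a sponsor or DMC decision override the investigator's DLT entry, and SAP 8.2 has population exclusions reviewed case by case before data release.

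**3. Which deaths are affected?**
- Not those with earlier qualifying PD, which is already the event. A single PD qualifies if it is the last tumour assessment.
- Not those more than 65 days (2 × 29 + 7) after the last assessment, which are censored whatever the cause.
- What remains is a myeloma death with no qualifying PD, within 65 days of the last assessment, coded to another term.

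**4. Which endpoints?** TTP, DoR and DoCB. PFS, EFS and TTNT count death without regard to cause.

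**5. Illustration under a constant hazard.** Let f be the share of events that are deaths without prior PD, and q the share of those coded to another term. Both are assumptions. Losing a fraction fq of events scales the hazard by (1 − fq), and so the median by 1/(1 − fq). The small loss of follow-up time is ignored.

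| f | q | fq | 1/(1 − fq) − 1 |
|---|---|---|---|
| 5% | 50% | 0.025 | 2.6% |
| 10% | 50% | 0.05 | 5.3% |
| 20% | 50% | 0.10 | 11.1% |
| 20% | 75% | 0.15 | 17.6% |

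**6. Illustration with 9 subjects.** Assume TTP events at 1, 2, 3, 4, 5, 7, 9, 12 and 15 months and no other censoring. With all counted, the 6-month event-free estimate is 4/9 = 44%, and the median (first time at or below 50%) is 5 months. Now censor one of the five early events about one cycle (0.92 months) before it occurred:
- Event at month 1: 8 subjects remain at risk, and events at 2, 3, 4 and 5 give 4/8 = 50%. The median stays at 5.
- Event at month 5: four events among 9 give 5/9 = 56%. The median becomes 7.
- The other three cases give 51%, 52% and 53%, with a median of 7.

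One such death therefore raises the 6-month estimate by about 6 to 11 percentage points in this invented example.

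**The case against.** The best defence is that few deaths can be involved. Response is assessed on Day 1 of each cycle and about every 4 weeks in follow-up, an unconfirmed last PD still counts, and late deaths are censored under any rule. Protocol 12.1 also says that signs and symptoms of an event already reported need not be reported separately, which favours recording the disease itself. The two-term rule is prespecified and reproducible, whereas classifying deaths brings judgement into a study in which nobody is blinded. PFS has the same presentations as TTP and counts deaths regardless of cause, and SAP 10.2 tabulates SAEs leading to death by preferred term.

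Most of this stands and limits the size of the point. It does not remove it. DoR and DoCB have no all-cause counterpart, and a gap between TTP and PFS also contains deaths that truly had other causes.

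Three stronger readings are tempting:
- **Dictionary version.** MedDRA 20.1 is "updated to the newest version 23.0 for the follow-up analyses", so a reader might infer that a death could change status between analyses. The documents do not show that coding to either term differs between the versions.
- **A sizeable bias.** A reader might take 11% or 18% as the expected distortion. Those figures come from assumed f and q, and nothing in the documents supports particular values.
- **A ready-made variable.** Protocol 12.1 requires the cause of death in SAE follow-up. The documents do not show that it is a field in the analysis database.

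Protocol 11.1.1 also counts death as progression without regard to cause. A cause-based rule would still differ from that text, so this point does not settle that difference.

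**Conclusion.** The point holds in limited form. Following SAP 7.3.3.3 literally would censor a myeloma death coded to a complication in TTP, DoR and DoCB, and the direction of the bias is upward. Its size is unknown, because the documents give neither the number of deaths without qualifying PD nor how fatal events were coded. The percentages above show sensitivity only and are not estimates.

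TTP and DoR are secondary and DoCB is additional; all are descriptive. No primary endpoint, error rate or sample size is touched. This is a worthwhile low-cost improvement to the event definition.

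**What to change.** Amend SAP 7.3.3.3 as follows:

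- Before data release, classify every death without prior documented PD as due to progression or not, whatever its preferred term, using the cause of death obtained in SAE follow-up. If that is not an eCRF field, take it from the SAE records.
- List each such death with its preferred term and classification.
- Carry the same classification into the follow-up analyses.
- Keep the two-term rule as a sensitivity analysis for TTP, DoR and DoCB.

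The cost is a short SAP change, review of what should be a few deaths, and some retrieval work if the cause is held only in the SAE records. The downside is some judgement in an open-label study. The listing and the sensitivity analysis make that judgement visible.
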